### **Aim 2**

Aim 2 measures, collected through the electronic medical record and using publicly available U.S. Census data, will include:

- *Patient-level data*: age, sex, race/ethnicity, education, marital status, cancer type, cancer stage, health insurance (e.g., Medicare, Medicaid, commercial);
- *Clinician-level data*: years in practice and patient panel size;
- *Practice-level data*: setting (community vs. hospital-based), urban vs. non-urban location, and health insurance mix;
- *Ecologic-level data* linked at the patient- and practice-level, including median income and educational attainment.

### **3. Genetic Testing:**

Not applicable

### **4. Use of Deception:**

Not applicable

### **5. Statistical Analysis:**

#### **Aim 1**

The design is a three-arm randomized trial, resulting in three independent study arms: (1) usual practice, (2) encounter-based PRO monitoring with patient reminders and triage nurse alerts, (3) remote PRO monitoring with patient reminders and triage nurse alerts. Implementation and effectiveness outcomes will be assessed across arms. The main comparison for the purposes of power calculations will be Arm 2 vs Arm 1. Multivariable linear regression will be used to model patient PRO adherence as a function of nudge exposure (i.e., study arm assignment). Covariates will be assessed across study arms and included in the model if unbalanced across arms.

Significance will be determined using the z-score corresponding to each of the estimated effects, using a two sided type 1 error of 5%. All enrolled patients will be included in the intention-to-treat analysis.

The secondary outcomes will be similarly modeled except using logistic models as appropriate for binary outcome variables. All hypothesis tests will use a two-sided alpha of 0.05 as the threshold for statistical significance.

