**METHODS:**

**1. Study Instruments:**

We do not anticipate the use of study instruments beyond the PRO questionnaire **[Appendix 1]**, which is already administered in routine practice. Any additional study instruments will be submitted to the IRB as a modification prior to use.

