### **Power and Sample Size**

For our primary comparison of patient-level adherence across study arms, we expect to have 80% power to detect a 14.5 percentage point difference in patient-level adherence, assuming baseline adherence rates of 0.50 (SD 0.40) [based on our preliminary data], a two-sided alpha of 0.05, and a mean of approximately 3 opportunities for each patient to complete the survey. Based on prior trends in Beacon plan treatment starts in 2022, this assumes accrual of approximately 100 patients per month for three months totaling approximately n=300 patients. Over the course of the pragmatic trial, enrollment exceeded expectations at both participating sites. As such, the target accrual was updated to total approximately 480 patients.

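### The primary adherence model makes no planned use of pre-randomization PRO completion, which costs precision (an amount the documents do not fix) but not validity

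*Combined protocol and SAP*

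**What the plan says.** The primary outcome is each patient's proportion of expected questionnaires completed over about 3 months. Under Statistical Analysis, Aim 1, "Multivariable linear regression will be used to model patient PRO adherence as a function of nudge exposure (i.e., study arm assignment". Covariates are compared across arms and enter the model only where an imbalance is seen; the section names none.

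The one list of patient-level variables is under Data Collection, Aim 2: "age, sex, race/ethnicity, education, marital status, cancer type, cancer stage, health insurance". It contains no measure of earlier questionnaire completion, and neither do the moderators in the Aim 2 analysis. Hypothesis H2b refers to baseline adherence rates, but no section defines or collects a baseline value for the individual patient. The baseline in Power and Sample Size is a group figure: "assuming baseline adherence rates of 0.50 (SD 0.40) [based on our preliminary data".

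Study Instruments describes the questionnaire as one "which is already administered in routine practice", and Data Collection names the electronic medical record and other routine databases as sources. Patients enter when they start a new line of intravenous chemotherapy or immunotherapy at a participating site.

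**The concern.** The outcome is a repeated behaviour, and the same behaviour was open to some of these patients before randomization. A patient's own earlier completion is often a strong predictor of later completion. It is fixed before allocation, so adjusting for it does not bias the arm effect and can narrow its confidence interval.

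The plan's covariate rule is not built to capture this. It selects on observed imbalance, not on prognostic value, and it can act only on variables that someone has extracted. At stake is the precision of the main comparison, Arm 2 vs Arm 1.

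**Working it through.** **Inputs from the plan.** Mean 0.50, SD 0.40 (variance 0.16), a mean of about 3 opportunities per patient, two-sided alpha 0.05, 1:1:1 allocation, about 300 patients at first and about 480 now (100 and 160 per arm).

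**The plan's own figure.** The plan claims "80% power to detect a 14.5 percentage point difference" with about 300 patients. The detectable difference is (1.960 + 0.842) × 0.40 × √(2/n).
- n = 100 per arm: 15.8 points; power for 14.5 points is 72.7%, so the stated 80% does not reproduce. It needs 120 per arm.
- n = 160 per arm: 12.5 points; power for 14.5 points is 90.0%.

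The second line is the reference for what follows.

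**Between-patient variance, assuming exactly 3 opportunities each.** With τ² the variance of patients' underlying completion probability:
- 0.16 = τ² + (0.25 − τ²)/3, so τ² = 0.115
- Within-patient correlation = 0.115/0.25 = 0.46
- Stable share of outcome variance = 0.115/0.16 = 72%

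**Predictive value of history, assuming the probability is unchanged across the new line.** For k prior opportunities, R² = τ⁴ / {[τ² + (0.25 − τ²)/k] × 0.16}.

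| Prior opportunities | R² among patients with history |
|---|---|
| 1 | 0.33 |
| 2 | 0.45 |
| 3 | 0.52 |
| 6 | 0.60 |
| 12 | 0.66 |

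At k = 3 the correlation between prior and in-trial proportions is 3 × 0.46/(1 + 2 × 0.46) = 0.72, and its square is 0.52.

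**Allowing opportunities to vary.** The plan gives only a mean. Assume an even spread over 1 to 5, unrelated to the patient's completion probability:
- Mean of 1/m = (1 + 0.5 + 0.333 + 0.25 + 0.2)/5 = 0.457
- τ² = (0.16 − 0.25 × 0.457)/(1 − 0.457) = 0.084
- Within-patient correlation = 0.084/0.25 = 0.34
- With history spread the same way, R² = (0.084/0.16)² = 0.28

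**Effect on Arm 2 vs Arm 1 at 160 per arm.** The share with history is an assumption. The first two rows come from simulation (4,000 trials; prior proportion plus a no-history indicator). The third multiplies R² = 0.28 by the share.

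| Case | 25% with history | 50% | 75% |
|---|---|---|---|
| 3 before and 3 after, stable: variance reduction | 12% | 25% | 38% |
| 3 before and 3 after, half of patients draw a new probability: variance reduction | 3% | 6% | 9% |
| 1 to 5 opportunities, stable: variance reduction | 7% | 14% | 21% |

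The detectable difference is 12.5 × √(variance ratio). In the favourable row the ratios 0.879, 0.747 and 0.616 give 11.7, 10.8 and 9.8 points. In the unstable row the ratios 0.974, 0.941 and 0.909 give 12.4, 12.2 and 11.9 points.

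**The case against.** The strongest reply is that nothing here is an error. A linear comparison of randomized arms without this covariate is valid, there is no bias or type 1 error problem, and the current target already gives about 90% power for the plan's 14.5 points. That stands, and it limits the point to an improvement in efficiency.

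Three stronger readings are tempting, and the documents do not support them.
- A reader might infer that the plan's SD by itself shows that history could explain up to half of the outcome variance. It does not. The figure of about one half also needs exactly 3 opportunities before and after and a stable completion probability. Nor is it a ceiling: perfect knowledge of that probability would give 72% under the same assumptions. One prior opportunity gives 33%, and varying opportunities about 28%.
- A reader might infer that the record holds this history for every patient. Eligibility requires only a new line of therapy, so first-line patients and patients new to the site can enter. The share with history is not given.
- A reader might infer that the plan makes it impossible to select prior completion. The list lacking it belongs to Aim 2, and the Aim 1 rule names no covariates and so excludes none.

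It can also be said that no section describes how missed questionnaire offers are logged. That deserves a check. However, the primary outcome already requires a count of expected questionnaires in usual practice, so the same count over an earlier window is feasible in principle.

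**Conclusion.** The point holds as a missed gain in precision. No section plans to extract or use a patient's pre-randomization completion, and the only covariate rule waits for an observed imbalance. The validity of the primary analysis is not in question.

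The size is uncertain because three facts are missing: the share of patients with history, the number of prior questionnaires, and stability across a new line of therapy. For 25% to 75% with history, the variance reduction is about 12% to 38% in the favourable case and about 3% to 9% if completion is unstable; varying opportunities with stable completion falls between. These figures rest on a mean of 0.50 and an SD of 0.40 and apply to the encounter-based arms. Arm 3 is weekly, so about 3 opportunities does not describe it. The change is worth making because it is cheap, not because the trial depends on it.

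**What to change.** Apply the primary outcome's own definition of expected and completed questionnaires to a fixed look-back before randomization (for example 6 months). In Statistical Analysis, Aim 1, prespecify two terms for the primary model regardless of balance: the prior proportion completed, set to 0 where none was offered, and an indicator for none offered. Add both to the variables listed under Data Collection. Make the change before outcomes are examined by arm, and report the share of patients with history.

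The cost is one additional data extract and a short addition to the analysis text, with no patient contact. If few patients have history, the gain will be small.

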**STUDY PROCEDURES:**

**1. Detailed Description:**

Eligible patients will be identified pragmatically using the criteria listed above, and will be independently randomized to study arms using a three-arm design. A description of the three study arms follows:

- (1) Usual practice.** This arm will consist of encounter-based PRO monitoring, in which patients have an opportunity to complete PRO questionnaires via patient portal in advance of clinical encounters or via tablet during clinical encounters. While clinicians will be encouraged to view and discuss PROs with patients during clinical encounters, they will not be prompted to do so in real-time, nor will there be alerts for escalating symptoms.
- (2) Encounter-based PRO monitoring plus patient reminders and triage nurse alerts.** This arm consists of usual practice (described above) plus the addition of patient reminders to complete PRO questionnaires and triage nurse alerts for severe symptoms. Patient reminders will be operationalized through the Epic patient portal. Triage nurse alerts will be routed to Epic symptom management pools in response to a patient reporting moderate or severe symptoms. Patients will have the opportunity to decline or opt-out of triage nurse support. Clinical interventions stemming from triage nurse alerts will be up to the discretion of clinical teams – ie, clinical responses will be neither prescriptive nor mandatory. Notably, the entry point for triage nurse alerts (ie, Epic symptom management pools), as well as resultant clinical responses, are existing standard operating procedures/practices for patients reporting symptoms by phone.
- (3) Remote PRO monitoring plus patient reminders and triage nurse alerts.** This arm will consist of weekly PRO questionnaires administered via the patient portal, de-linked from clinical encounters. Patient reminders and triage nurse alerts will be operationalized as described in Arm (2).

We will use rapid cycle approaches (RCA) to optimize implementation strategies to ensure face validity and maximum effect. We will focus on optimizing content, messaging, and design. RCA procedures will involve design meetings with study team, discussions with administrators and clinicians who are members of our Implementation Lab, as well as piloting of nudges with potential participants to elicit feedback.

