**Aim 1**

The primary outcome will be PRO adherence, measured at the patient level as the proportion of expected PRO questionnaires completed per patient. Secondary specifications will include:

- % patients completing at least one PRO questionnaire during study period
- % patients completing at least one PRO questionnaire per month during the study period

Secondary implementation outcomes will include:

- % patients with at least one note documenting PROs during study period
- % patients with at least one note documenting PROs per month during study period
- For Arms 2-3 only: time to alert response

Secondary effectiveness outcomes will include:

- Symptom burden, measured as a composite and for each PRO/symptom
  - a. For Arms 2-3 only: % patients who trigger alert
- Acute care utilization, measured as % patients with ED visit or hospitalization
- Treatment delays/modifications, measured as % patients with treatment delay/modification
- Duration of therapy

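### The primary regression names no robust or arm-specific variance, although adherence rests on about 3 questionnaires in Arms 1-2 and about 13 in Arm 3; the Arm 2 vs Arm 1 standard error is therefore likely misstated, in a direction the documents do not settle.

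*Combined protocol and SAP*

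**What the plan says.** Data Collection, Aim 1 defines the outcome: "The primary outcome will be PRO adherence, measured at the patient level as the proportion of expected PRO questionnaires completed per patient". Statistical Analysis, Aim 1 gives the model: "Multivariable linear regression will be used to model patient PRO adherence as a function of nudge exposure (i.e., study arm assignment"; covariates enter if they are unbalanced across arms. The same section says "The main comparison for the purposes of power calculations will be Arm 2 vs Arm 1" and sets the test: "Significance will be determined using the z-score corresponding to each of the estimated effects, using a two sided type 1 error of 5" per cent. It names no variance estimator, whether pooled, robust, weighted or arm-specific. It does not say whether Arm 2 vs Arm 1 is read from a three-arm model or from a fit to those two arms alone.

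Power and Sample Size says "we expect to have 80% power to detect a 14.5 percentage point difference in patient-level adherence", "assuming baseline adherence rates of 0.50 (SD 0.40"), with "a mean of approximately 3 opportunities for each patient to complete the survey". The number of opportunities is not broken down by arm.

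Study Procedures, Detailed Description ties questionnaires in Arms 1 and 2 to clinical encounters, by portal beforehand or by tablet at the visit. For Arm 3: "This arm will consist of weekly PRO questionnaires administered via the patient portal, de-linked from clinical encounters". Subject Follow-up gives about 3 months per patient.

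**The concern.** Ordinary least squares estimates one residual variance and uses it for every contrast. The variance of a per-patient proportion has a between-patient part and a within-patient part, and the second shrinks as the number of questionnaires grows. Here that number differs about fourfold between arms by design (13/3 = 4.3), and the route of completion differs too. There is no reason to expect equal variances.

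In a three-arm model, Arm 3 enters the standard error of Arm 2 vs Arm 1 although, covariates aside, it tells us nothing about that difference. If Arm 3 varies less than the other two arms, the main z-score is inflated and its interval too narrow. If Arm 3 varies more, the test is conservative. Contrasts involving Arm 3 err the opposite way. With equal allocation the relative error does not depend on sample size, so raising the target from 300 to 480 does not remove it. At stake is whether the stated 5% holds for the main comparison.

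**Working it through.** **1. The plan's own power figure.** With 300 patients allocated 1:1:1 there are 100 per arm. SE = 0.40 × √(2/100) = 0.0566; 0.145/0.0566 = 2.563; power = Φ(2.563 − 1.960) = 72.7%, not the stated 80%. At 480 patients (160 per arm), SE = 0.40 × √(2/160) = 0.0447; 0.145/0.0447 = 3.242; power = Φ(1.282) = 90.0%. The mismatch at 300 is a separate matter and does not affect what follows, which uses only the mean, the SD and the number of opportunities.

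**2. Questionnaires per patient.** Weekly over about 3 months gives about 13 in Arm 3 (derived, not stated). The 3 opportunities cannot be an average over all arms on that schedule: Arm 3 alone would contribute 13/3 = 4.3 to the mean. I take 3 to describe Arms 1 and 2.

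**3. Variance by arm.** For mean p, m questionnaires and within-patient correlation ρ, Var = p(1−p)[ρ + (1−ρ)/m].
- Arms 1-2: 0.40² = 0.16 = 0.25[ρ + (1−ρ)/3], so ρ = (0.64 − 1/3) × 1.5 = 0.46.
- Arm 3, **assuming** the same p and ρ: 0.25[0.46 + 0.54/13] = 0.1254, SD 0.354.

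**4. Effect on Arm 2 vs Arm 1.** Pooled variance = (0.16 + 0.16 + 0.1254)/3 = 0.1485, SD 0.385. Model SE / true SE = √(0.1485/0.16) = 0.963, which is 3.7% too small. Type 1 error = 2[1 − Φ(1.960 × 0.963)] = 5.9%.

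**5. Range.** The documents give no mean, SD or correlation for Arm 3, so every row below is an assumption. Unless noted, Arms 1-2 have mean 0.50 and SD 0.40, and Arm 3 has p = 0.50, ρ = 0.46 and m = 13.

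| Scenario | Arm 3 SD | SE ratio | Type 1 error |
|---|---|---|---|
| Base case | 0.354 | 0.963 | 5.9% |
| Arm 3 m = 8 | 0.363 | 0.970 | 5.7% |
| Arm 3 m unlimited | 0.339 | 0.952 | 6.2% |
| Arm 3 p = 0.70 | 0.325 | 0.941 | 6.5% |
| Arm 3 p = 0.80 | 0.283 | 0.913 | 7.4% |
| Arm 3 ρ = 0.61 | 0.400 | 1.000 | 5.0% |
| Arm 3 ρ = 0.70 | 0.425 | 1.021 | 4.5% |
| Arm 3 ρ = 0.80 | 0.451 | 1.045 | 4.1% |
| Arms 1-2 p = 0.80 (ρ = 0.46, m = 3) | 0.354 | 1.037 | 4.2% |

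The break-even solves 0.64 = ρ + (1−ρ)/13, so ρ = (0.64 − 1/13) × 13/12 = 0.61.

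If opportunities in Arms 1-2 vary around 3 (assumed uniform on 1 to 5), the mean of 1/m is 0.457. Writing τ² for the between-patient variance, 0.16 = τ² + (0.25 − τ²) × 0.457 gives τ² = 0.084. The Arm 3 variance is then 0.084 + (0.25 − 0.084)/13 = 0.097 (SD 0.31), the ratio √[(0.32 + 0.097)/3/0.16] = 0.932, and the type 1 error 6.8%.

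**6. Arm 3 contrasts.** In the base case the true variance averages (0.16 + 0.1254)/2 = 0.1427, so the SE ratio is √(0.1485/0.1427) = 1.02, or 2% too large. With ρ = 0.80 in Arm 3 (variance 0.2038) it is √(0.1746/0.1819) = 0.98, or 2% too small.

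**7. Simulation check.** Beta-binomial data, 160 per arm, 20,000 replicates (Monte Carlo SE √(0.05 × 0.95/20,000) = 0.0015). In the base case the type 1 error was 6.2% pooled and 5.3% with variances not pooled across arms. With Arm 3 ρ = 0.75 it was 4.2% (0.0415) and 5.0% (0.0495). With Arm 3 p = 0.70 it was 6.4% and 5.0%.

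**8. Power.** At 160 per arm and a true 14.5-point difference, the base-case pooled test rejects with probability Φ[(0.145 − 1.960 × 0.0431)/0.0447] = 91.2%, against 90.0% with arm-specific variances. The extra 1.2 points come only from the looser type 1 error.

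**The case against.** A reader might infer that the plan uses one pooled variance, and that Arm 3 is less variable by design because more questionnaires enter each proportion, so that the Arm 2 vs Arm 1 standard error is simply too small and the z-score inflated. The documents do not support that.

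First, no variance estimator is stated. A single three-arm least-squares fit is the default reading, supported by the reference to a z-score for each estimated effect, but it remains an inference. A fit to Arms 1 and 2 alone, or robust errors, would remove the problem for the main comparison.

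Second, more questionnaires shrink only the within-patient part of the variance. Patients in Arms 1 and 2 can use a tablet at the visit; Arm 3 is administered through the portal, away from encounters. Patients who do not use the portal could score near zero while engaged users score high. As an illustration with assumed values, 35% at zero and 65% with mean 0.77 and SD 0.25 give mean 0.50 and variance 0.65 × (0.25² + 0.77²) − 0.50² ≈ 0.176, SD about 0.42. The pooled standard error is then about 1.6% too large.

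Third, the effect is small: under the plan's figures with 3 opportunities, equal means and equal correlation, the type 1 error cannot pass 6.2% however many questionnaires Arm 3 has.

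All three limits stand, and they rule out an asserted direction. What remains is that equal variance is not assured, the plan makes no stated allowance for this, and the estimator for the primary test is left open.

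**Conclusion.** The point holds as a gap in specification with a modest effect of undetermined sign. On the default reading, the Arm 2 vs Arm 1 standard error is likely misstated. It is about 4% too small (type 1 error about 5.9%) under the plan's mean, SD and 3 opportunities if Arm 3 shares the mean and the within-patient correlation of 0.46. It is 2% to 4% too large (type 1 error about 4% to 4.5%) if the Arm 3 correlation is 0.70 to 0.80. The sign changes at about 0.61.

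This rests on a three-arm model with a common variance, about 13 questionnaires in Arm 3, and 3 opportunities applying to Arms 1 and 2. The larger inflations (6.5% to 7.4%) need further assumptions about the Arm 3 mean or the spread of opportunities. An error of this size would change the conclusion only for a borderline result, so this is an inexpensive improvement and not a flaw that threatens the trial.

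**What to change.** Add to Statistical Analysis, Aim 1 that all linear-model contrasts on adherence use heteroscedasticity-robust (HC2 or HC3) standard errors or arm-specific residual variances, and that Arm 2 vs Arm 1 is taken from the three-arm model so fitted. Fitting Arms 1 and 2 alone would also protect the main comparison, but would leave contrasts with Arm 3 exposed.

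The cost is one phrase and one software option, with no new data or patients. The method is valid whichever way the Arm 3 variance falls; in the base case the only power given up is the 1.2 points that came from excess type 1 error. Fixing it in advance also removes a choice of estimator after the data are seen.

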## **OBJECTIVES:**

- (1) Evaluate the implementation and effectiveness of patient- and nurse-directed strategies across in-clinic and remote monitoring settings, using a three-arm pragmatic cluster RCT.
  - H1a: Nudges to patients and alerts to nurses will improve patient-level PRO completion and clinician-level PRO engagement
  
- (2) Evaluate moderators of implementation effects, using a quantitative evaluation of secondary data from the electronic health record, area-level data via geocoding, and clinician surveys.
  - H2a: The impact of nudges will be moderated by clinician, patient, and outer setting factors.
  - H2b: Baseline PRO adherence rates will differ by race, ethnicity, and socioeconomic status.
  - H2c: The nudge arms will not be significantly differentially effective across subgroups.

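### Must the plan say whether Arm 2 vs Arm 1 alone, or a benefit in either nudge arm, decides the adherence part of H1a?

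*Combined protocol and SAP*

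**What the plan says.** Under Objectives, the hypothesis is general and names no arm: "H1a: Nudges to patients and alerts to nurses will improve patient-level PRO completion and clinician-level PRO engagement".

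Under Study Procedures (Detailed Description), Arm 2 is usual practice with reminders and nurse alerts added. Arm 3 has the same reminders and alerts but a different schedule and setting: "This arm will consist of weekly PRO questionnaires administered via the patient portal, de-linked from clinical encounters".

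Statistical Analysis, Aim 1, fits a linear regression of adherence on assigned arm. It says "The main comparison for the purposes of power calculations will be Arm 2 vs Arm 1" and then, for the tests, "Significance will be determined using the z-score corresponding to each of the estimated effects, using a two sided type 1 error of 5" percent. No order of testing, adjustment, or split between confirmatory and supportive contrasts is given.

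Power and Sample Size uses the singular but names no pair: "For our primary comparison of patient-level adherence across study arms, we expect to have 80% power". It assumes "a mean of approximately 3 opportunities for each patient to complete the survey". On size it ends: "As such, the target accrual was updated to total approximately 480 patients".

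**The concern.** A three-level arm factor gives two effects against usual practice, and the plan tests each at two-sided 5%. Both nudge arms deliver what H1a is about, so either could be offered as evidence for it. The label of main comparison is tied to the power calculation, which sizes the trial but does not say which result confirms the hypothesis.

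The two contrasts could well disagree, because Arm 3 also changes the setting and frequency of the questionnaire. If only Arm 3 showed a benefit, the text would allow it to be called either confirmation of H1a or supportive evidence, and that choice could be made after seeing the results. Under an either-arm rule, the chance of a false claim of benefit would be nearly twice that of one contrast.

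**Working it through.** **Inputs from the plan.** Allocation 1:1:1 (Study Design); two-sided alpha 0.05 per effect (Aim 1); SD 0.40, difference 0.145, 80% power, about 300 patients, later about 480 (Power and Sample Size). Equal arms are assumed: 100 and then 160 each.

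**The plan's own power figure.** Power = Φ(0.145/SE − 1.96), with SE = 0.40 × √(2/n).
- n = 100 per arm: SE = 0.0566, 0.145/SE = 2.563, power 72.7%. The stated 80% is not reproduced; it needs 120 per arm (80.2%).
- n = 160 per arm: SE = 0.0447, 0.145/SE = 3.242, power 90.0%.

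This mismatch does not bear on the present point. With equal SDs, the error rates below depend only on alpha and allocation.

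**False benefit under each possible rule.** Assume no true differences and equal SDs. The two contrasts share Arm 1, so their correlation is 0.16/√(0.32 × 0.32) = 0.5.

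| What would count as support for H1a | Calculation | Chance of false benefit |
|---|---|---|
| Both nudge arms beat Arm 1 | 0.025 + 0.025 − 0.0454 | 0.5% |
| Arm 2 vs Arm 1 alone | 1 − Φ(1.96) | 2.5% |
| Nudge arms pooled vs Arm 1 | one test | 2.5% |
| Either nudge arm beats Arm 1 | 1 − Φ₂(1.96, 1.96; 0.5) | 4.54% |

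Counting both directions, the either-arm figure is 9.1%, against 5% for one contrast. Testing each contrast at two-sided 0.025 would bring the either-arm figure to 2.3%.

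**If the Arm 3 SD differs.** The documents give no SD for weekly remote adherence, so 0.30 to 0.45 is an assumption. The planned linear regression uses one pooled variance, (0.16 + 0.16 + s²)/3, where s is the Arm 3 SD.
- s = 0.30: pooled variance 0.1367. The Arm 2 vs Arm 1 statistic has variance 0.32/(2 × 0.1367) = 1.171. Arm 2 vs Arm 1 alone gives 3.5%; either arm gives 4.9%.
- s = 0.45: pooled variance 0.1742, and the same statistic has variance 0.919. Arm 2 vs Arm 1 alone gives 2.0%; either arm gives 4.4%.

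The either-arm figure stays between 4.4% and 4.9%. The departure of the single contrast from 2.5% comes from the pooled variance, not from the number of contrasts.

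**Cost of joint adjustment.** At 160 per arm, SD 0.40 and 14.5 points, power per contrast falls from 90.0% to 84.2% at two-sided 0.025 (Bonferroni), or to 88.2% with Holm if both effects are 14.5 points. Under the pooled-variance regression with an Arm 3 SD of 0.45, Bonferroni power for Arm 3 vs Arm 1 is 80.2%. Adjustment is affordable but not free.

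**Which reading the text favours.**
- For Arm 2 vs Arm 1: it is called the main comparison; the power section speaks of one primary comparison; about 3 opportunities per patient fits encounter-based arms better than weekly questionnaires over 3 months (about 13); and Arm 2 differs from Arm 1 only by the reminders and alerts.
- Against: the label is limited to power, the primary comparison is said to run across arms, and the objective covers in-clinic and remote settings.

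**The case for a change.** The strongest case for a change is that a decision rule should be written before results are seen, and here it would take a sentence or two. Naming Arm 2 vs Arm 1 as the sole confirmatory contrast would cost that contrast no power. The counter-evidence in the text is inference: neither the power label nor the assumed number of opportunities says what confirms H1a.

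Much of this stands. The text does leave the rule open, and one clarifying sentence would do no harm. But it does not show an error in the analysis. The 4.5% belongs to an either-arm rule that the plan never states. Of the four plausible rules, one raises the error rate above that of a single contrast, two leave it unchanged and one lowers it. The case for joint control is also weaker than when several versions of one treatment are tested. Arm 3 differs from Arm 1 in schedule, setting and number of expected questionnaires as well as in nudges, so it asks a different question of a shared control. Separate 5% tests are then a common and defensible choice.

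**Conclusion.** No change is called for. The plan leaves a gap in wording that an analyst would sensibly fill by treating Arm 2 vs Arm 1 as the test of the reminders and alerts, and Arm 3 vs Arm 1 as the separate question of remote monitoring with them. On that reading the false-benefit chance is the planned 2.5% (5% two-sided), given similar SDs across arms. Only an either-arm rule would raise it, to 4.5% (9.1% two-sided), or 4.4% to 4.9% under the planned regression for an assumed Arm 3 SD of 0.30 to 0.45. Whether to adjust for that is a trade-off for the sponsor.

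The two contrasts come from one model. If both are reported with their p-values, a reader wanting joint control can hold the smaller p-value to 0.025. The case to watch is a report that declares H1a confirmed on Arm 3 alone with a p-value between 0.025 and 0.05. This conclusion covers only the adherence part of H1a, not clinician engagement.
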